6.4 Variables

Variables to be collected in pre-screening log by the pharmacist:

- Patient age in years and months;
- Reason for non-inclusion to the investigation (if applicable). For example: antibiotics, previous cough treatment;
- Reason for refusal to participate in the investigation (if applicable).

Variables to be collected in screening log by the investigator:

- Patient age in years and months;
- Reason for non-inclusion to the investigation (if applicable);
- Approximate date of dry cough start;
- PCQ-score (based on the recall of the night prior inclusion) – only patients with a score of 3 or above at least for 3 of the 5 items of PCQ are to be included (see section 6.9.1).

Table 2: Variables to be collected at patient enrolment

Sociodemographic data and dispensing modalities	Age in years and months
(To be recorded by the investigator in the eCRF)	Rank among siblings
	Weight and height
	Sex and geographic region
	Did the patient receive a doctor's prescription for Petit Drill? (Yes/No)
Baseline medical data	Pre-existing medical conditions
(To be recorded by the investigator in the eCRF)	Investigator's assessment of patient's condition Acute dry cough Yes/No
	Approximate date of dry cough start
	Prior treatments for ongoing cough
	Ongoing, non-interfering medications
Associated symptoms at baseline	
	Fever (Yes/No)
	Runny nose (Yes/No)
	Congestion (Yes/No)
	Sore throat (Yes/No)
	Ear Pain (Yes/No)
	Sensation of pain or more frequent crying than usual (Yes/No)
	Digestive symptoms (vomiting or diarrhoea) (Yes/No)
	Reduced appetite (Yes/No)
PCQ (to be recorded by the parent/legal representative in the NursTrial® app with the help of the investigator)	
CONFIDENTIAL	V6.0 #Sans suivi modifications#26-MAR-2024
	Page 31/65

Q1. How frequent was your child's cough last night?	0- Not at all
	1- Occasionally
	2- A little
	3- Somewhat
	4- Very much
Q2. How much did last night's cough affect your child's ability to sleep?	5- Extremely
	0- Not at all
	1- Occasionally
	2- A little
	3- Somewhat
Q3. How much did last night's cough affect your ability to sleep?	4- Very much
	5- Extremely
	0- Not at all
	1- Occasionally
	2- A little
Q4. How severe was your child's cough last night?	3- Somewhat
	4- Very much
	5- Extremely
	0- Not at all
	1- Occasionally
Q5. How bothersome was last night's cough to your child?	2- A little
	3- Somewhat
	4- Very much
	5- Extremely
	0- Not at all
PAC-QoL (to be recorded by the parent/legal representative in the NursTrial® app with the help of the investigator)	
1-Were you worried/concerned about your child's cough becoming worse?	1- very, very worried and concerned
	2- very, worried and concerned
	3- fairly, worried and concerned
	4- somewhat worried and concerned
	5- a little worried and concerned
	6- hardly worried and concerned
	7- not worried and concerned
2-Did you feel tired or exhausted because of your child's cough?	1- all the time
	2- most of the time
	3- quite often
	4- some of the time
	5- once in a while
	6- hardly any of the time
	7- none of the time
3-Were you worried/concerned about the effects of your child's cough on him/her?	1- very, very worried and concerned
	2- very worried and concerned
	3- fairly, worried and concerned
	4- somewhat worried and concerned
	5- a little worried and concerned
	6- hardly worried and concerned
	7- not worried and concerned
4-Were you worried/concerned about the cause of your child's cough?	1- very, very worried and concerned
	2- very worried and concerned

Pierre Fabre

CLINICAL INVESTIGATION PLAN (CIP)

Table 3: Variables to be collected during patient follow-up by the parent/legal representative

Outcome	Suggested schedule	Variables
For primary outcome and secondary performance outcome 1: PCQ global and scores of the 5 items Q1, Q2, Q3, Q4 and Q5	D2 – first thing in the morning after 1 st night of treatment D3 – first thing in the morning after 2 nd night of treatment D4 – first thing in the morning after 3 rd night of treatment	0 – Not at all 1 – Occasionally 2 – A little 3 – Somewhat 4 – Very much 5 – Extremely
For secondary performance outcome 2: Daily cough severity	D2 – first thing in the morning after 1 st night of treatment D3 – first thing in the morning after 2 nd night of treatment D4 – first thing in the morning after 3 rd night of treatment	0-100 evAS value
For secondary clinical benefit outcome: PAC-QoL	D4 – first thing in the morning after 3 rd night of treatment	1- all the time or very, very worried and concerned 2- most of the time or very, worried and concerned 3- quite often or fairly, worried and concerned 4- some of the time or somewhat worried and concerned 5- once in a while or a little worried and concerned 6- hardly any of the time or hardly worried and concerned 7- none of the time or not worried and concerned
For secondary safety outcome: number and percentage of AEs, including device deficiencies (DD) (to be completed by the investigator during an interview with the parent/legal representative)	Once a day, at a time of choice and at investigation end.	All AEs during the 3-day period will be asked to be reported by the patient, whether they think it is related to the investigational device or not. Once a day the following questions will be asked. 
• Today did your child experience any sort of illness or negative effects (whether related to the Syrup or not)? Yes/ No If yes, please contact the investigator.
		CONFIDENTIAL V6.0 #Sans suivi modifications#26-MAR-2024 Page 34/65

Pierre Fabre

CLINICAL INVESTIGATION PLAN (CIP)

Outcome	Suggested schedule	Variables
Adherence	At least once a day or at each intake	
How many times in the previous 24 hours did your child use Petit Drill? (Insert a single digit number)
 
For each dose, please give the approximate time: HH:MM
 
If Petit Drill is stopped before the recommended treatment duration of 3 days, please specify the reason:
 
Cough improvement / Cough worsening / Other /Other specify

Parent Satisfaction with Petit Drill Syrup Use	At study end (after 3 days of use)	
 How would you rate the quality of therapeutic management your child received? (Excellent/ Good/ Fair/ Poor) To what extent did this treatment meet your child's needs? (Almost all of my child's needs were met/ Most of my child's needs were met/ Only few of my child's needs were met/ None of my child's needs were met) Would you recommend this treatment to another parent? (No, definitely not/ Not really/ Yes, generally/ Yes, definitely) How satisfied are you with information received from the IFU to use this treatment? (Quite dissatisfied/ Indifferent or mildly dissatisfied/ Mostly satisfied/ Very satisfied) In a general sense, was it easy to use this treatment? (No, definitely not/ Not really/ Yes, generally/ Yes, definitely) Did your child seem to like the taste of the syrup? (No, definitely not/ Not really/ Yes, generally/ Yes, definitely)

Pierre Fabre

CLINICAL INVESTIGATION PLAN (CIP)

Table 4: Variables to be collected by the investigator in case of AE or DD occurring during patient follow-up

Outcome	Suggested schedule	Variables
For secondary safety outcome: number and percentage of AEs, including device deficiencies (DD) (to be completed by the investigator during an interview with the patient/legal representative)	Anytime during patient's follow-up	
Select all that apply
 
 Any new illness or symptom (diagnosed or undiagnosed) Any worsening of an existing illness or symptoms (diagnosed or undiagnosed) Any medical interventions (such as vaccination, surgery etc.) Any usual or unusual health-related event (such as loss of appetite, teething pain, reflux etc.) 
For each event, please provide the following details:
 
 Describe event in own words Date of event start: DD/MM/YYYY Action taken in response to event (select all that apply): medications given/ hospitalization/ visit to a healthcare professional (HCP)/ no action taken Assessment of seriousness: 
 Did the event lead to death? Yes/ No Did the event lead to a life-threatening illness or injury? Yes/ No Did the event lead to permanent impairment of a body part or body function? Yes/ No Did the event lead to hospitalization or prolongation? Yes/ No Did the event require a medical or surgical intervention to prevent life-threatening illness or injury or permanent impairment to a body part or body function? Yes/ No Did the event lead to development of a chronic disease? Yes/No Outcome at the end of the 3-day follow-up (select only ONE): Ongoing/ Completely Resolved/ Resolved with after-effects/ Not sure 
 Please select all that apply regarding the use of Petit Drill 
 The external packaging was damaged upon reception The bottle cap was not sealed, or damaged upon reception The bottle was damaged upon reception/during use The pipette was damaged upon reception The pipette was damaged during use I used more or less than the prescribed dose because it was confusing to use the pipette

Pierre Fabre

CLINICAL INVESTIGATION PLAN (CIP)

	
I used more or less than the prescribed dose because the IFU was not clearThe syrup fell into eyes or ears during useMy child was taking another medication while using the syrupIf yes, please mention the medicationMy child may be allergic to the syrupSomeone else, other than my child used the syrup (including accidental use)Child accidentally accesses the bottleI did not use the designated pipetteSyrup reached air tubePipette reached air tube
--	---

CONFIDENTIAL

V6.0 #Sans suivi
modifications#26-MAR-2024

Page 37/65

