The patient's follow-up will last as long as he/she receives Petit Drill but will not exceed 3 days and 3 nights. Indeed, to stay close to real-word condition of use of Petit Drill, the treatment duration is recommended as per IFU but not imposed in the present clinical investigation. However, the parent must specify reason for stopping the treatment in the App.

During the follow-up, the patient's parent will have to complete the daily questionnaire and record Petit Drill intake in the App. Parents will be asked to inform the investigator of any adverse event as soon as possible.

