14.3 Reporting of medical device cases

All AEs and DD that would occur during the 3-day follow-up period will be asked to be reported by the parents/guardians via the mobile application daily, whether they think it is related to the investigational device or not. The questionnaire to be used by the parents/guardians is provided in Table 3 above.

The questionnaire will be formulated such that the parents/guardians will be able to describe the AE to allow the determination of seriousness and causality by the investigator.

Following a declaration, an automatic notification will be sent to the investigator who will then be required to follow-up on the event.

The following would be defined as elements that could be a potential AE during the 3-day follow-up:

- Any new illness or symptom (diagnosed or undiagnosed);
- Any worsening of an existing illness or symptoms (diagnosed or undiagnosed);
- Any usual or unusual health-related event (such as loss of appetite, teething pain, reflux etc.).

Investigator's responsibility:

All these foreseeable events can be mitigated by carefully reading the IFU and by storing the device out of the reach of children and in suitable conditions as detailed in the IFU.

All AE, SAE and DD observed during the study must be reported in the eCRF by the investigator. Each AE must be assessed for seriousness, severity and causality by the investigator.

For AE or SAE including DD whether or not considered as related to the device or to the procedure the investigator will complete immediately and within 3 calendar days the form (FORM_CVI_6585) "Solicited adverse event collection form" and collect the results of the carried-out examinations and the reports of hospitalisation if applicable.

In case the investigator is aware of any new information, it should be reported to the sponsor.

Contractor's responsibility:

The contractor conducting the study will be required to provide the following information that has been brought to his attention about the investigational device within 1 business day after its acknowledgment in the eCRF:

- Any AE or SAE including DD which arises from the use of Petit Drill;
- Any SAE considered as related to the procedure of the study.

The safety information will be communicated to Pierre Fabre Vigilance department no later than 24 hours upon its reception by the contractor, through the form (FORM_CVI_6585) "Solicited adverse event collection form", which will be sent by email: [contact].

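### The daily adverse-event question does not name worsening of symptoms, and a stop for cough worsening has no stated route to adverse-event assessment, so overall AE frequency in SO7 may be under-counted

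*Protocol*

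**What the plan says.** **What counts as an event.** Protocol section 14.3 lists, among potential AEs, "Any worsening of an existing illness or symptoms (diagnosed or undiagnosed"). Table 4, the investigator's form for AEs and device deficiencies, carries the same item.

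**What the parent is asked.** Section 14.3 names the questionnaire in Table 3 (section 6.4) as the parents' reporting instrument. Its safety row asks "Today did your child experience any sort of illness or negative effects (whether related to the Syrup or not"), on the schedule "Once a day, at a time of choice and at investigation end". A parent who answers yes is told to contact the investigator. Section 6.10 also asks parents to tell the investigator promptly of any adverse event.

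**What happens next.** Section 14.3 says: "Following a declaration, an automatic notification will be sent to the investigator", who must then follow up.

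**Where worsening is named to the parent.** The adherence row of Table 3 asks for the reason if the syrup is stopped before three days, with the choices "Cough improvement / Cough worsening / Other /Other specify". Section 6.10 makes the answer mandatory: "However, the parent must specify reason for stopping the treatment in the App".

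**How long follow-up lasts.** Section 6.10: "The patient's follow-up will last as long as he/she receives Petit Drill", with a ceiling of three days and three nights.

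**What is reported.** SO7 (section 6.3.2) gives AE frequency, severity and causality. It also gives a count of relevant AEs: serious events, device-related events and events of special interest. Section 7.2 attaches 95% confidence intervals to the safety outcomes.

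**The concern.** The question that feeds SO7 is narrower than the protocol's own description of an AE. Inclusion criteria IC4 and IC5 admit only children with an acute cough and a score of at least 3 on at least three of the five PCQ items, so every child is already ill on day 1. Asked whether the child has had any illness or negative effect today, a parent may take a worse cough to be the illness already reported and answer no. The same parent may then choose *Cough worsening* as the reason for stopping. The sponsor would hold a record of something section 14.3 calls a potential AE, with no stated step that brings it to the investigator. A stop for any other health event has to go under *Other*, because the list has no adverse-event choice.

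Two things are at stake: the overall AE frequency in SO7, and prompt investigator contact with children who stop because they are worse. Section 5.3 says that clinical safety data on this device are being obtained in a clinical investigation for the first time. Later correction is unlikely: section 6.11 foresees no monitoring procedures, section 8.1.3 no source documents, and section 8.2.1 little scope to rectify parent-entered data once locked.

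**Working it through.** **1. The entries side by side**

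| Protocol entry | Names worsening? | Stated link to the investigator |
|---|---|---|
| 14.3, list of potential AEs | Yes | Definition only |
| Table 3, safety row (daily and at end) | No | If yes, parent contacts investigator; 14.3 adds automatic notification after a declaration |
| Table 3, adherence row (stop reason, mandatory under 6.10) | Yes | None stated |
| Table 4 (investigator form) | Yes | Used once an AE or deficiency has surfaced |

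The wording that would prompt a yes is in the definition and in the form completed afterwards, but not in the question that decides whether the form is opened. The one parent-facing field that names worsening has no stated route onward. Section 11 describes a notification too, but for device deficiencies and adverse device effects.

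**2. The denominator**

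The protocol gives no AE or stopping rate. The only figures to work with are the sample sizes in section 7.4, and both reproduce:

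- Evaluable: n = z² × p(1 − p) / d² = 1.95996² × 0.5 × 0.5 / 0.07² = 195.99, rounded up to 196.
- Enrolled: 196 / (1 − 0.20) = 245.

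**3. Weight of one missed child**

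- 1/245 = 0.41 percentage points.
- 1/196 = 0.51 percentage points.

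**4. Illustration under assumed rates**

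The share of children who stop for worsening is an assumption, taken as 1%, 5% or 10% of 245 (2, 12 or 24 children). The table gives exact (Clopper-Pearson) 95% intervals for the proportion with such an event, by how many reach the AE listing.

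| Assumed share | All captured | Half captured | None captured |
|---|---|---|---|
| 1% | 2: 0.10% to 2.92% | 1: 0.01% to 2.25% | 0: 0% to 1.49% |
| 5% | 12: 2.56% to 8.40% | 6: 0.90% to 5.25% | 0: 0% to 1.49% |
| 10% | 24: 6.38% to 14.22% | 12: 2.56% to 8.40% | 0: 0% to 1.49% |

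At an assumed 5%, losing half moves the estimate from 12/245 = 4.9% to 6/245 = 2.4%. The table shows sensitivity only. It does not predict how many events will be lost.

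**5. Which SO7 figures are exposed**

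Overall AE frequency is exposed directly. The relevant-AE count changes only if the worsening is serious, is judged device-related or is of special interest. Section 14.2 classes cases whose relatedness cannot be assessed as possibly related, so some unassessed events could belong there, but a non-serious worsening judged unrelated does not.

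**The case against.** The strongest reply is that a safety pathway exists and is asked of everyone. This is largely right, and it rules out several stronger readings.

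- **That worsening is recorded only in the adherence field.** A reader might infer this, but the same parent also gets the safety question every day and is asked to report any AE.
- **That no question follows an early stop.** Follow-up tied to treatment suggests it, but the safety row is also due at investigation end, and section 6.3.1 collects the final PCQ the morning after the last treatment day. Early stopping may shorten the run of daily questions; it does not remove the closing one.
- **That the stop reason triggers no alert.** The protocol does not say so. It is silent on whether the answer counts as a declaration, and section 8 leaves data-collection procedures to a data management plan and operational documents that are not shown.
- **That the broad question already covers worsening.** Read literally, a child whose cough is worse has an illness that day, and the answer should be yes. Some parents will read it so. The row's label also speaks of an investigator interview, in which Table 4 would raise worsening. But the same row tells the parent to contact the investigator after a yes, and sections 8.1.2 and 14.3 place reporting in the app, so the interview cannot be relied on to prompt a parent who answered no.
- **That the protocol contradicts itself between SO5 and SO7.** It does not: SO5 reports the number of administrations, not stop reasons. Nor is *Other* left unexplained, since it has a field to specify.

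Worsening will also show in the daily PCQ and cough-severity scores, but no section routes those to AE assessment either. What remains is a question narrower than the definition it serves, and a relevant answer with no stated destination. Both are fixed in sections 6.4 and 14.3, so this is not detail properly left to an analysis plan.

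**Conclusion.** The point holds as a gap in safety capture. The Table 3 safety question omits a category that section 14.3 counts as a potential AE, and the mandatory stop reason that does name it is not stated to lead to AE assessment. Overall AE frequency in SO7 may be under-counted, and investigator contact may be delayed for some children who stop because they are worse.

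The size cannot be estimated from the protocol. Each missed child is 0.41 points of 245; any larger figure rests on an assumed stopping rate and an assumed share of parents who answer no. A reader might take 2% to 5% of 245 (5 to 12 children) as the expected loss, but the protocol gives no such rate, and those children would be missed only if none of their parents used the safety question. Nor does the text support saying that every SO7 percentage is biased low: the relevant-AE count is affected only under the conditions in step 5. The conclusion assumes that some parents regard a worse cough as the same illness, which is plausible when all children enter with a cough. No sample-size figure depends on it.

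**What to change.** 1. In Table 3 and section 14.3, state that a stop for *Cough worsening*, or for an *Other* reason that describes a health event, counts as a declaration, with the same automatic notification and with Table 4 completed by the investigator.
2. Add an adverse-event choice to the list of stop reasons.
3. Extend the daily question so that it also asks about worsening of existing symptoms, in line with section 14.3.
4. Reconcile the stop-reason listing with the AE listing before database lock.

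The cost is a change to the app configuration and a few more investigator calls, in a process that already requires follow-up of declarations. The reported AE rate may rise slightly, because events that fit the protocol's own description would be counted more completely.

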6.3.2 Secondary outcome(s)

- SO1. Baseline clinical and sociodemographic characteristics of children will be summarized using descriptive statistics;

Secondary criteria related to the performance and the clinical benefit of Petit Drill will be described as follow:

- SO2. Score global and score of the 5 items of PCQ (Q1: cough frequency, Q2: sleep disturbance of the child, Q3: sleep disturbance of the parent, Q4: cough severity, Q5: degree of bothersomeness to the child) will be described after 1, 2 and 3 day-treatment with Petit Drill. The percentage of children with a 3 point-decrease of PCQ total score from baseline at 1 and 2 day-treatment with Petit Drill will be described;
- SO3. Daily cough severity will be measured using visual analogue scale (VAS) ranging from 0 (no cough) to 100 (worst cough) in response to "Yesterday, how was the cough of

my child during the day?", measured VAS after 1, 2 and 3 day-treatment with Petit Drill. the evolution of scores from baseline will be described;

•SO4. Scores of the Parent-proxy Children's Acute Cough-Specific Questionnaire PAC-QoL (global and dimensions) will be collected at baseline (D1) and after 3 day-treatment with Petit Drill (morning D4), or on the next morning of the last day of treatment. The evolution of scores from baseline will be described.

Secondary criteria related to the assessment of use and the safety of Petit Drill will be described as follow:

- SO5. The mean (SD) number of times Petit Drill was administered in each 24-hour period from the first (D1) to the third (D3) day of treatment initiation will be described;
- SO6. Parent's satisfaction with Petit Drill use will be described using a questionnaire, and responses measured using Likert scales. Responses will be presented as percentages;
- SO7. Safety will be assessed by the analysis of:
 - Adverse events (frequency, severity, emergence, and causal relationship of adverse events) tabulated according to IMDRF terms (International Medical Device Regulators Forum, Annex E). Number and percentage of relevant AEs during treatment with Petit Drill, defined as all SAEs or AEs related to the device, and any AEs of special interest;
 - Number and percentage of device deficiencies.

6.3.3 *Exploratory outcomes*

- SO8. The percentage of children receiving Petit Drill with or without physician prescription will be described by two age groups: from 6 months to 12 months old and from 13 months old to 6 years of age;

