6.10 Procedures

Pre-screening

Pharmacist will briefly present the clinical investigation to the parent/legal representative who purchases Petit Drill for his/her child/relative from 6 months to 6 years old. The pharmacist will also orally verify the eligibility criteria (Cf. sections 6.9.1 and 6.9.2).

If the parent does not want to participate but gives the pharmacist his/her agreement, the pharmacist will record in a pre-screened log child's age and gender, and main reason of parent's refusal.

If the parent is interested, the pharmacist will provide the study information note and transfer the parent's name and contact information to the clinical investigation centre (CEN Expérimental) via a dedicated page of the study website.

Inclusion visit

Upon receipt of a pre-screen patient on the study website, the parent/legal representative will be contacted to take part to the remote inclusion visit with an Investigator (General Practitioner) of CEN Experimental, scheduled within the day of Petit Drill delivery.

Before proceeding with the signing of the consent, the investigator will first ensure that the parent/legal representative is duly informed. Consent will be electronically signed using a solution (DocuSign) whose functionality meets recommended expectations of the Guidance on computerized systems and electronic data in clinical trials (EMA/INS/GCP/112288/2023). The informed consent process is detailed in section 13.

In non-single-parent households, the informed parent who signed the consent will remain the one who completes the study data in the ePRO App NursTrial®.

If several children are eligible in the same household, an algorithm will randomly select one of them. Then, the Investigator will check the inclusion and exclusion criteria, and proceed to the patient's enrolment.

The Investigator will record the necessary study data in the e-CRF (socio-demographics, baseline medical data). A Clinical Research Associate will help the parent download the NursTrial® App on their smartphone and create their personal access. Then, the parent will complete the study questionnaires in the App.

Study follow-up

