14.2 Assessment of AE and SAEs

Each AE must be assessed for seriousness, causality, severity by the investigator or another suitably qualified physician in the research team who is trained in recording and reporting AEs.

The expectedness assessment will be performed by the sponsor.

The investigator and sponsor will make an assessment of seriousness (as defined above).

The investigator and sponsor will also make an assessment of the causal relationship with the study product, and/or associated products, and/or study procedures according to the following definitions:

1. **Not related:** where an event is not considered to be related to the study product and/or associated products and/or study procedures.
2. **Possibly related:** the relationship with the use of the investigational device or comparator, or the relationship with procedures, is weak but cannot be ruled out completely. Alternative causes are also possible (e.g., an underlying or concurrent illness/ clinical condition or/and an effect of another device, drug or treatment). Cases where relatedness cannot be assessed, or no information has been obtained should also be classified as possible.
3. **Probably related:** the relationship with the use of the investigational device or comparator, or the relationship with procedures, seems relevant and/or the event cannot be reasonably explained by another cause.
4. **Causal relationship:** the adverse event is associated with the investigational device, comparator or with procedures beyond reasonable doubt when:
 - the event is a known side effect of the product category the device belongs to or of similar devices and procedures;
 - the event has a temporal relationship with investigational device use/application or procedures;
 - the event involves a body-site or organ that:
 - o the investigational device or procedures are applied to;
 - o the investigational device or procedures have an effect on.
 - the adverse event follows a known response pattern to the medical device (if the response pattern is previously known);
 - the discontinuation of medical device application (or reduction of the level of activation/exposure) and reintroduction of its use (or increase of the level of activation/exposure), impact on the adverse event (when clinically feasible);
 - other possible causes (e.g., an underlying or concurrent illness/ clinical condition or/and an effect of another device, drug or treatment) have been adequately ruled out;

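### Adverse-event onset is listed as a date only while each dose gets an approximate clock time, so the listed onset field cannot order a D1 event against the first dose

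*Protocol*

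**What the plan says.** - **Outcome.** SO7 in Protocol section 6.3.2 analyses "Adverse events (frequency, severity, emergence, and causal relationship of adverse events". It also reports a count restricted to the treatment period: "Number and percentage of relevant AEs during treatment with Petit Drill, defined as all SAEs or AEs related to the device", together with events of special interest. Section 7.2 plans 95% confidence intervals for the safety outcomes.
- **Onset of an event.** Table 4 in section 6.4 lists "Date of event start: DD/MM/YYYY" and a narrative ("Describe event in own words"). It lists no clock time and no item on order relative to dosing. The daily question in Table 3 also works by day: "Today did your child experience any sort of illness or negative effects (whether related to the Syrup or not".
- **Time of a dose.** The adherence row of Table 3 asks: "For each dose, please give the approximate time: HH:MM".
- **Causality.** One criterion for a causal relationship in section 14.2 is that "the event has a temporal relationship with investigational device use/application or procedures".
- **What happens on D1.** Section 6.10 has the remote inclusion visit "scheduled within the day of Petit Drill delivery", and section 6.3.1 has the baseline recorded at inclusion on D1. Inclusion, first dose and an early event can therefore share one calendar date.

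**The concern.** Emergence is a statement about order: the event began at or after first exposure. The protocol collects one side of that comparison by approximate clock time and the other by calendar date. The mismatch matters on D1. These children are already ill, and D1 is also the day on which an immediate reaction to the syrup would first show. A rash dated D1 has the same recorded onset whether it was there before the first dose or appeared soon after it.

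An analysis convention does not fully repair this. A statistical analysis plan can say how to classify onsets on the first-dose date, but it cannot recover an order that was never recorded. Later retrieval is also unlikely: section 8.1.3 foresees no source documents, section 6.11 no monitoring procedures, and section 8.2.1 locks parent-reported data at study end. Section 5.3 adds that this is the first clinical investigation to yield safety data on the product.

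**Working it through.** The plan states no figure on this point, so the check is mainly a comparison of the listed variables.

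**1. Resolution of the two clocks**

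| Item | Where | Resolution |
|---|---|---|
| Dose | Table 3, adherence row | approximate HH:MM, each dose |
| Daily adverse-event question | Table 3, safety row | day |
| Event onset | Table 4 | DD/MM/YYYY |
| Event narrative | Table 4 | free text, time not requested |

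**2. What the onset date can settle**

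- Onset dated before D1: before the first dose.
- Onset dated D2 or later: after the first dose, if that was given on D1.
- Onset dated D1: undetermined.
- Interval from the preceding dose to onset, on any day: not obtainable from the onset field. This bears on the temporal criterion in section 14.2, not on emergence.

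**3. What other records add**

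- The baseline checklist (Table 2) covers fever, runny nose, congestion, sore throat, ear pain, pain or unusual crying, digestive symptoms and reduced appetite. It has no rash item. Section 6.10 does not say whether the first dose comes before or after the visit, so the checklist is not certain to describe the child before exposure.
- The interview may establish the order, but no listed field requires it.
- Section 14.2 says that cases where relatedness cannot be assessed are to be classed as possibly related. Unknown order could therefore move an event towards the device-related count.

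**4. Illustration of size, with assumed counts**

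The safety population is every child who received the syrup. Assume n = 245, the planned enrolment. The exact (Clopper-Pearson) 95% upper limit for x events is the 97.5% quantile of Beta(x + 1, n − x). For x = 0 this is 1 − 0.025^(1/245).

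| Events of 245 | Exact 95% upper limit |
|---|---|
| 0 | 1.49% |
| 1 | 2.25% |
| 3 | 3.54% |

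Moving from 0 to 3 events multiplies the upper limit by 3.54/1.49 = 2.4.

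With a larger assumed count, suppose 12 children have an event and 4 of these are D1 events of unknown order. The emergent count then lies between 12 − 4 = 8 and 12:

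| n | 8 events | 12 events |
|---|---|---|
| 245 | 3.3% (1.4 to 6.3) | 4.9% (2.6 to 8.4) |
| 196 (= 245 × 0.8) | 4.1% (1.8 to 7.9) | 6.1% (3.2 to 10.5) |

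None of these counts is a forecast.

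**The case against.** **Table 4 is not the whole record.** It lists neither a severity grade nor a causality category, yet sections 14.2 and 14.3 require both to be assessed, with severity recorded in the eCRF. The investigator also completes FORM_CVI_6585 for each event, and its content is not shown. This stands: the finding concerns the listed variables, and a time field may exist elsewhere.

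**The follow-up window may exclude events before dosing.** Section 6.9.5 starts follow-up at initiation of the syrup, although section 8.1.2 starts it at inclusion. This helps only in part, because deciding whether a D1 event falls inside the section 6.9.5 window needs the same missing order.

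**Prior illness is partly captured.** The checklist covers common symptoms, including vomiting, and gastrointestinal pathology is an exclusion criterion. This stands for the listed symptoms.

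**Emergence is not causality.** A reader might infer that counting every D1 onset as emergent attributes earlier illness to the device. It does not, since relatedness is judged separately by investigator and sponsor. An event known to precede the first dose would not normally be called related. For the relevant-event count, the exposure is mainly unrelated serious events, events of special interest, and events classed as possibly related because the order is unknown.

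**The same-day rule belongs in the statistical analysis plan.** This stands: the missing definition of emergent is not a finding. What remains is the data item that any such rule would need.

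**Conclusion.** The point holds as a minor gap in data collection. From the onset field listed in Table 4, an event dated D1 cannot be ordered against the first dose, and no event can be timed relative to a dose. Other records may recover this only in part. The effect is limited to D1 events in the emergence tabulation and to the timing evidence for causality. The primary outcome and sample size are untouched.

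Three stronger readings are not supported:

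- That D1 events cannot be placed at all. The interview, the checklist or the unseen form may place some of them.
- That doses are timed to the minute. The form asks for an approximate time.
- That a third of the observation period is compromised because D1 is one of three days. Emergent status would change only for events that began on D1 before the first dose.

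The documents give no adverse-event rate, so the effect cannot be sized. The limits of 1.5%, 2.3% and 3.5% assume 245 treated children and hypothetical counts.

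**What to change.** In Table 4 and on the eCRF adverse-event page:

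- Replace the onset field with: *Date and approximate time of event start (DD/MM/YYYY HH:MM, or unknown)*.
- Add the item: *Started before / after first dose of Petit Drill*.

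The second item answers the emergence question directly when the parent cannot give a time. The first lets the dose log already collected in Table 3 support the temporal criterion in section 14.2. If FORM_CVI_6585 already holds equivalent fields, it is enough to cite them in Table 4 and carry them into the database.

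The cost is one time field and one tick box in an interview that the investigator already conducts. The small downside is that times will be approximate and sometimes unknown.
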